4.12.2. Body Weight, Height, and BMI

Descriptive statistics on change from baseline in the body weight (kg), height (cm), and BMI will be displayed at each visit.

The change in weight or height percentiles calculated by using Centers for Disease Control and Prevention (CDC) growth chart [CDC] will be analyzed similarly for subjects < 18 years old at baseline.

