3.3. Clinical Endpoints

Primary

• Safety profile characterized by type, frequency, severity, timing, and relationship to ataluren of any adverse events or laboratory abnormalities

Secondary

- Changes in FEV₁, FVC, and FEF₂₅₋₇₅ as assessed by spirometry
- Rate, incidence, and duration of pulmonary exacerbations (modified Fuchs criteria)
- Incidences, rates, and durations of interventions (eg, antibiotic use and hospitalization) and disruptions to daily living (eg, missed school or work) resulting from pulmonary symptoms
- Changes in CFQ-R domains
- Changes in body weight and BMI
- New Pseudomonas aeruginosa lung infection
- Pre-dose ataluren plasma concentrations prior to morning ataluren administration at each clinic visit as assessed by a validated bioanalytical method
- Change from baseline in other safety parameters (eg, vital signs)

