11.4.6. Secondary Variables

11.4.6.1 Spirometry

Both absolute change and relative change in %-predicted FEV_1 from Baseline at each visit will be summarized descriptively. Pediatric equations for calculating %-predicted FEV_1 [Wang 1993] will be used from 6 to <16 years of age for female subjects and from 6 to <18 years of age for male subjects. For males or females >18 years of age, an adult equation for calculating %-predicted FEV_1 [Hankinson 1999] will be used. Each %-predicted FEV_1 will be based on the height value obtained at the same study visit. The changes from baseline to each post-baseline visit will be analyzed using paired t-tests.

Above analyses will be repeated for FVC and FEF₂₅₋₇₅.

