14.4.4. Weight/Body Mass Index

Patients with CF are almost universally underweight when compared to healthy individuals of the same gender and age. Contributing factors include malabsorption due to pancreatic insufficiency and high work of breathing [Zemel 1996]. There is an association between worsening lung function and malabsorption, and evidence that nutritional intervention may improve pulmonary function [Milla 2004].

Given this knowledge, assessment of body weight and BMI during the course of this Phase 3 extension study is planned. While changes in these parameters are quite nonspecific, they constitute simple-to-assess outcomes of general well-being that complement data obtained from other efficacy measures.

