2.3.3. Tertiary Endpoints

- Change from baseline in other safety parameters (eg, vital signs, body weight, height, BMI, 12-lead ECG measurements, renal ultrasound)
- Incidence of new *Pseudomonas aeruginosa* lung infection
- Pre-dose ataluren plasma concentrations prior to morning ataluren administration at each clinic visit as assessed by a validated bioanalytical method

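### BMI change is summarised raw and pooled over children and adults, so normal growth is mixed into a measure tied to the general well-being objective

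*SAP*

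**What the plan says.** SAP 4.12.2 gives one rule for all ages: "Descriptive statistics on change from baseline in the body weight (kg), height (cm), and BMI will be displayed at each visit". It then adds a growth-referenced summary, limited to patients under 18 at baseline: "The change in weight or height percentiles calculated by using Centers for Disease Control and Prevention (CDC) growth chart [CDC] will be analyzed similarly". It plans no BMI percentile and no z-score of any kind. Protocol 11.4.7.1 also plans only by-visit values and changes.

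Protocol 3.3 lists "Changes in body weight and BMI" among the secondary endpoints. Protocol 14.4.4 explains their purpose: "they constitute simple-to-assess outcomes of general well-being that complement data obtained from other efficacy measures". The general well-being objective is kept in SAP 2.2.2. SAP 2.3.3 places the measures in the tertiary group: "Change from baseline in other safety parameters (eg, vital signs, body weight, height, BMI, 12-lead ECG measurements, renal ultrasound".

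The population includes growing children. The paediatric spirometry equations in Protocol 11.4.6.1 "will be used from 6 to <16 years of age for female subjects and from 6 to <18 years of age for male subjects", and Protocol 14.1.2 expects many enrolled patients not to be sexually mature.

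**The concern.** BMI changes with age in children, so a raw change over a year or more contains growth as well as any nutritional change. Every patient in this open-label extension takes ataluren, so no concurrent group shows what growth alone would have done. Pooling children with adults makes the mean depend on the age mix too.

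The SAP accepts age standardisation elsewhere: age- and height-specific blood pressure percentiles for patients under 18 (4.12.1), CDC percentiles for weight and height (4.12.2) and %-predicted FEV1 (4.11.1). BMI is the exception, and no reason is given. At stake is whether the BMI table can say anything about well-being in children.

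A second, weaker issue is the percentile scale. Towards the bottom of a growth chart, equal gains in SD units become smaller gains in percentile points. Protocol 14.4.4 makes this relevant: "Patients with CF are almost universally underweight when compared to healthy individuals of the same gender and age".

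**Working it through.** The plan states no figure for this endpoint, so there is nothing to reproduce. Two checks follow.

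**1. Growth drift in pooled raw BMI**

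Longest possible follow-up:
- Protocol section 1 dates the first Study 021 dose to 15 August 2014, with 48 weeks of treatment. Adding 336 days gives a first extension entry of about 17 July 2015.
- SAP 2.1 ends the study on March 2, 2017. From 17 July 2015 that is 594 days, and 594/7 is about 85 weeks. The planned 96 weeks is therefore out of reach, visit windows aside.

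Assumptions (neither is in the documents): BMI growth in patients under 18 of 0.3 to 0.8 kg/m2 a year; share of patients under 18 of 30% to 50%; no drift in adults and no drug effect.

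Formula: pooled drift = annual rate × (weeks × 7/365.25) × share under 18.

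| Follow-up | Years | Low: 0.3 × years × 30% | High: 0.8 × years × 50% |
|---|---|---|---|
| 48 weeks | 0.92 | 0.08 kg/m2 | 0.37 kg/m2 |
| 85 weeks | 1.63 | 0.15 kg/m2 | 0.65 kg/m2 |

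Per child, before pooling, the drift is 0.28 to 0.74 kg/m2 at 48 weeks and 0.49 to 1.30 at 85 weeks.

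**2. Behaviour of the percentile scale**

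Formula: percentile = 100 × Φ(z). A gain of 0.5 SD is assumed from several assumed starting points. The last column divides by the movement from z = 0. Differences are taken before rounding.

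| Baseline z | Baseline percentile | Gain in points | Relative to z = 0 |
|---|---|---|---|
| 0 | 50.00 | 19.15 | 100% |
| -0.5 | 30.85 | 19.15 | 100% |
| -1 | 15.87 | 14.99 | 78% |
| -1.5 | 6.68 | 9.18 | 48% |
| -2 | 2.28 | 4.41 | 23% |

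For a group with z-scores normally distributed about μ with SD 1 (also assumed), the mean percentile is 100 × Φ(μ/√2). The mean gain for a 0.5 SD shift is then 13.8 points at μ = 0, 12.2 at -1, 9.5 at -1.5 and 6.6 at -2. A group mean is compressed less than an individual far down the chart.

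**The case against.** The strongest reply is that little rests on this table. SAP 4.2 calls all analyses descriptive, SAP 2.3.3 ranks BMI as tertiary, SAP section 1 lets the SAP supersede the protocol, and Protocol 14.4.4 itself calls changes in weight and BMI nonspecific. No test or decision threshold depends on them. This stands, and it limits the point to interpretation.

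Other outputs also cover children: raw weight and height change, weight and height percentiles, the percentage weight-change categories in SAP 4.12.1 and by-subject listings (SAP 4.1). These would show that a child gained or lost weight. None of them adjusts BMI for growth. The percentage categories are not growth-adjusted either, and the optional age-group description in SAP 4.12.1 is for vital signs, a list that omits BMI.

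A reader might infer that the planned percentiles would hardly register change in this population. The documents do not support that. They give no baseline z-score or percentile. The statement in Protocol 14.4.4 concerns weight in patients with CF generally, gives no degree of deficit and does not mention height. Compression is negligible near z = -0.5 and becomes severe only at about z = -2 or below.

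A reader might also work out the drift over the planned 96 weeks. Termination rules that out. On the estimated 14-month recruitment in Protocol section 1, the last entrants would have only about 24 weeks, so late visits will hold few patients.

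**Conclusion.** The point holds for BMI. As written, the plan mixes growth into BMI change in children, and no other planned table removes it. On the stated assumptions the pooled drift is about 0.08 to 0.37 kg/m2 at 48 weeks and 0.15 to 0.65 at about 85 weeks. The growth rates and the paediatric share are assumptions, so these figures show scale and are not estimates for this cohort.

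For percentiles, the supportable statement is narrower: they give equal SD gains unequal weight, to an unknown extent here. That is a reason to add z-scores; it does not show that the percentiles are wrong. Nor do the documents say that a rise in BMI will be claimed as benefit; the table simply could not bear that reading in children. No error rate or sample size is affected.

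**What to change.** Amend SAP 4.12.2 as follows:

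- For patients under 18 at baseline, add change from baseline in CDC BMI-for-age z-score at each visit.
- For the same patients, report weight and height z-score change alongside the planned percentiles. The percentiles can stay, since dropping them would only be a presentation preference.
- Show raw BMI and raw weight change separately for patients under 18 and 18 or over, the age groups already defined in SAP 4.6.
- State that any comment on general well-being in children will rest on the BMI z-score.

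The cost is a few lines of SAP text and a little programming. Height and weight are scheduled at every visit (Protocol 8.2.8, with the within-14-days baseline exception in Table 3), age and gender are baseline variables (SAP 4.6), and the CDC reference is already cited (SAP section 7). SAP section 1 provides for amendment before the databases are locked.

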4.12.3. Electrocardiographic Analyses

The assessments in electrocardiographic (ECG) will be performed and interpreted locally for clinical significance.

Shift tables for the interpretation of the 12-lead ECG results ("normal", "abnormal, not clinically significant") will be presented to show the change in results from baseline ("normal", "abnormal, not clinically significant", "abnormal, clinically significant") to each visit ("normal", "abnormal, not clinically significant", "abnormal, clinically significant").

4.12.4. Renal Ultrasound

Shift tables for renal ultrasound results ("normal", "abnormal, not clinically significant", "abnormal, clinically significant") will be presented by treatment group to show the change in results from baseline ("normal", "abnormal, not clinically significant", "abnormal, clinically significant") to each visit ("normal", "abnormal, not clinically significant").

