Laboratory evaluation for adrenal function (cortisol, renin and aldosterone) will be performed at screening to determine normal clinical function. The results of placebo-controlled clinical trials with ataluren in nmCF and nmDBMD showed no meaningful imbalances in adrenal laboratory assessments between the ataluren and placebo arms; therefore, regular monitoring of function is not warranted and will not be performed routinely during study participation. However, adrenal function (via these or other parameters) may be tested in patients with evidence of adrenal dysfunction as clinically indicated.

The incidence of new onset nephrolithiasis was similar in both the ataluren and placebo arm in the previous double-blind study (4.2% on ataluren vs 3.4% on placebo). All cases involving the diagnosis of urinary tract calculi should be reported as adverse events of special interest to the CRO Pharmacovigilance Unit (see Section 9.1.2). Once it has been documented that a patient has symptomatic nephrolithiasis, determining the type of stone and the possible presence of either biochemical abnormalities or underlying conditions that predispose to stone formation are essential for guiding therapy to prevent recurrent disease. Patients should be encouraged to retrieve stones they pass or have removed for analysis. Analysis of the stone is an essential part of the evaluation. All patients presenting with their first stone should undergo a focused history, radiologic imaging, and at least a limited laboratory evaluation. A complete metabolic evaluation, in addition to the basic laboratory testing, is indicated in all patients with multiple stones at first presentation, in patients with a strong family history of stones, and in individuals with active stone disease, which is defined as recurrent stone formation, enlargement of existing stones, or the recurrent passage of gravel. The purpose of the focused history is to identify stone risk factors, such as a family history of stone disease and certain dietary habits. Adverse dietary habits include:

- Low fluid intake or a high fluid loss (eg, from sweating or gastrointestinal losses), which leads to a lower urine output and, therefore, a higher concentration of lithogenic factors.
- Higher animal protein diet, which can lead to hypercalciuria, hyperuricosuria, hypocitraturia, and elevated urinary acid excretion.
- Higher salt diet, which increases urinary calcium excretion.

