8.2.13. Renal Ultrasound

An ultrasound to examine the kidneys and collecting system will be performed at Screening/Baseline (Visit 1), Week 48 (Visit 5) and Week 96 (Visit 9 – End of Treatment/Premature Discontinuation) visit. The ultrasound examination will be performed according to local standards and a final interpretation and report will be provided by a local qualified expert. The findings will be captured in source documents and within the CRF.

A follow-up renal ultrasound may also be performed at any time during the study as clinically indicated at the discretion of the investigator. The PTC medical monitor must be informed via e-mail that an additional renal ultrasound was obtained and the serious adverse event reporting process should be followed, if applicable.

8.2.14. 12-Lead ECG

A 12-lead ECG will be obtained at Screening/Baseline (Visit 1), Week 48 (Visit 5), Week 96 (Visit 9 – End of Treatment/Premature Discontinuation) visit, and at the Post-Treatment Visit (4 weeks post discontinuation of study drug). The ECG will be performed and interpreted locally for clinical significance. The findings will be captured in source documents and with the CRF.

A follow-up ECG may also be performed at any time during the study as clinically indicated at the discretion of the investigator. The PTC medical monitor must be informed via e-mail that an additional ECG was obtained and the serious adverse event reporting process should be followed, if applicable.

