- Serum Blood Urea Nitrogen: Considering its role in maintaining urine-concentrating ability, urea has major importance in renal physiology and its clinical measurement as a marker of renal dysfunction is long established. In the context of nephrotoxicity, elevations in BUN suggest disruption of tubular integrity [Vonderscher 2007]. In the nonclinical mouse studies of ataluren in which nephrosis were observed, BUN was elevated in some of the affected animals, confirming that this marker should also be measured in clinical studies of ataluren. Monitoring serum BUN, like monitoring creatinine, provides an additional frame of reference relative to other markers assessed within this study and in other studies of known nephrotoxicants. However, an elevation in BUN is not a specific signal of renal tubular injury, but also may reflect compromised renal tubular blood flow due to depressed cardiac output, medications, or dehydration [Guignard 2004, Stevens 2007]. For these reasons, a BUN increase ≥1.5 x ULN should prompt a review of potential pre-renal, renal, and post-renal causes for the abnormality as well as consideration of potential interruption/modification of study drug dosing.
- **Renal Ultrasound**: In considering the markers to be used for decision-making within the study, renal ultrasound is proposed because it is the central imaging modality for assessing the anatomy of the kidneys and urinary tract in children. The test can detect changes in kidney size, assess parenchymal cystic or mass lesions, evaluate the renal vasculature, and assess the collecting system [Avni 2004]. Renal ultrasound is a routine component of diagnostic algorithms for follow-up of serum or urinary abnormalities suggesting renal dysfunction [Barratt 2004] and will be among the diagnostic testing performed for this

protocol as part of the assessment for such findings. It is safe, painless and convenient, providing advantages over contrast-enhanced computed tomography (CT) scanning (which has contrast-mediated nephrotoxicity and radiation risks) and magnetic resonance imaging (MRI) (which requires contrast administration and potential sedation in young children). Obtaining a baseline ultrasound enhances the sensitivity of subsequent ultrasonography, offering context for any potential abnormalities emerging during study drug treatment. An end-of-study ultrasound offers further reassurance that the kidneys remain anatomically normal at the completion of this protocol.

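### SAP 4.12.4 names three renal ultrasound categories overall and at baseline but only two at each visit, so a shift table built to that list has no cell for a clinically significant post-baseline scan

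*SAP*

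**What the plan says.** SAP 4.12.4 is a single sentence with three category lists.

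- The tabulated variable has three categories: "Shift tables for renal ultrasound results ('normal', 'abnormal, not clinically significant', 'abnormal, clinically significant') will be presented by treatment group".
- Baseline has the same three: "to show the change in results from baseline ('normal', 'abnormal, not clinically significant', 'abnormal, clinically significant".
- The post-baseline side has two: "to each visit ('normal', 'abnormal, not clinically significant". The list closes at that point.

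The section just before it, SAP 4.12.3 on ECG, has the same structure. Its opening list has two categories: "Shift tables for the interpretation of the 12-lead ECG results ('normal', 'abnormal, not clinically significant') will be presented". Its baseline list has three, and so does its post-baseline list: "to each visit ('normal', 'abnormal, not clinically significant', 'abnormal, clinically significant".

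Protocol 8.2.13 sets the scans: "An ultrasound to examine the kidneys and collecting system will be performed at" Screening/Baseline, Week 48, and Week 96 or premature discontinuation. SAP 2.3.3 names renal ultrasound among the tertiary safety endpoints. On the purpose of the last scan, Protocol 14.2.4 says: "An end-of-study ultrasound offers further reassurance that the kidneys remain anatomically normal at the completion of this protocol".

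**The concern.** The each-visit list defines the columns of the table. The category left out of it is the one a safety reader looks for. A programmer who follows the list has nowhere to put a patient whose Week 48 or end-of-treatment scan is read as abnormal and clinically significant.

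The kidney is the organ in which this gap is least welcome. Protocol 14.2.4 reports renal findings in mice with no no-effect level identified. It also reports seven serious renal events in Study 009 (3 acute renal failure, 3 renal failure, 1 hypercreatininemia), all in the ataluren arm. The 4.12.4 table is the only aggregate presentation of ultrasound in the SAP. If it cannot display a clinically significant result, it cannot help to show whether the kidneys stayed anatomically normal.

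The same sentence presents the table by treatment group. In a single-arm extension that phrase is undefined.

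**Working it through.** The documents give no figure to reproduce on this point. The check is a comparison of the lists and a count of cells. Below, NCS is abnormal but not clinically significant, and CS is abnormal and clinically significant.

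**Step 1. Categories named in each list**

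| Section | Opening list | Baseline list | Each-visit list |
|---|---|---|---|
| SAP 4.12.4, renal ultrasound | normal, NCS, CS | normal, NCS, CS | normal, NCS |
| SAP 4.12.3, ECG | normal, NCS | normal, NCS, CS | normal, NCS, CS |

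Each sentence has one short list, in a different position. In the ECG sentence the short list is the introductory one, and the two lists that define rows and columns are complete. In the ultrasound sentence the short list is the one that defines the columns.

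**Step 2. Cells per visit**

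Cells = baseline categories x post-baseline categories.

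- Each-visit list as written: 3 x 2 = 6.
- All three categories at each visit: 3 x 3 = 9.
- Difference: 9 - 6 = 3.

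**Step 3. Which cells are absent**

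- normal to CS: a new clinically significant finding
- NCS to CS: a new clinically significant finding
- CS to CS: a persisting clinically significant finding

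Two of the three are the only cells that could show a new clinically significant finding. Both scheduled post-baseline scans are affected. SAP 5.2 assigns an early termination visit to the next scheduled visit, so scans may appear under other weeks too. That does not change the count per visit.

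**Step 4. Is the omission deliberate?**

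SAP section 6 lists the analyses changed from the protocol and does not mention it. Nothing else in the SAP explains it. The opening list of the same sentence points the other way.

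**Step 5. Where else would a clinically significant scan appear?**

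- SAP 4.1 plans by-subject listings for every CRF module, and Protocol 8.2.13 has the ultrasound findings captured in the CRF.
- Protocol 11.4.7.1 has ultrasound results listed and abnormal ones followed up against other outcomes. SAP section 6 does not withdraw this.
- SAP 4.10.1 tabulates all treatment-emergent adverse events, tabulates renal events leading to special diagnostic evaluation, and gives several listings of renal adverse events. A scan finding reaches these only if it is reported as an adverse event.

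**Step 6. Treatment group**

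SAP 4.11.1 to 4.11.3 summarise efficacy overall and by preceding treatment group in study 021. The phrase in 4.12.4 may mean the same split, but it does not say so.

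**The case against.** The strongest reply is that this is a copying slip with little consequence. The sentence opens by defining the variable with all three categories, so its literal reading is a contradiction and not a clear instruction to build a 3 x 2 table. The ECG sentence beside it has the mirror-image slip. A programmer or a review of the table shells may well settle on 3 x 3. SAP 4.1 also asks for N, n and percentage, so patients left out would show as a shortfall. Ultrasound is a tertiary endpoint, and the listings and adverse event tables remain.

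Most of this stands, and it limits the size of the point. It does not remove it. The list that fixes the columns is the incomplete one, and a correct table would depend on someone departing from it. A shortfall in n would not separate a clinically significant scan from a missing one. Listings hold the individual results but are not a summary.

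Two stronger readings are tempting, and the documents support neither.

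- A reader might infer that the plan would report normal kidneys whatever the data show. The listings and adverse event outputs in step 5 rule that out for the planned reporting as a whole. No text tells anyone to recode a clinically significant scan into a milder column.
- A reader might apply the nephrolithiasis incidence in Protocol 6.3.2, "4.2% on ataluren vs 3.4% on placebo", to the enrolled number and call the result the count of hidden patients. That figure is new-onset stones in an earlier double-blind study, not a rate of clinically significant ultrasound readings. Protocol 6.3.2 and 9.1.2 also require urinary tract calculi to be reported as adverse events of special interest, so stones are among the findings least likely to be hidden.

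**Conclusion.** The point holds as an internal contradiction in SAP 4.12.4. Followed as listed, the renal ultrasound shift table loses 3 of 9 cells per visit. These are exactly the cells with a clinically significant post-baseline result, so the table could show neither a new nor a persisting finding of that kind. This rests on the wording alone and needs no assumption about event rates. The documents give no basis for a number of patients affected.

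The effect is limited to one tertiary safety summary. It is probably a drafting error and should be treated as a wording correction, not as a fault in renal safety monitoring. It is worth making before database lock because this is the only aggregate ultrasound output in the SAP and it concerns an organ that the protocol singles out for monitoring.

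A reader might also infer that the reference to treatment group is meaningless in a one-arm study and should be deleted. That goes too far. The SAP already uses the preceding study 021 group for other outcomes, and that split separates patients who received ataluren in study 021 from those who received placebo. The phrase needs a definition.

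**What to change.** - In SAP 4.12.4, add the clinically significant category to the each-visit list, so that rows and columns both have three categories.
- In SAP 4.12.3, add the same category to the opening ECG list, so that all three lists agree.
- In SAP 4.12.4, replace the reference to treatment group with overall and by preceding treatment group in study 021, as in 4.11.1 to 4.11.3. If something else is meant, state it.

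The cost is a few words in two adjacent sections and a check of the two table shells. No new data or analysis method is needed. SAP section 1 already provides for refinements by amendment before the databases are locked.
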